4.2 EXCLUSION CRITERIA

Any study subject who does **not** meet *all* of the above inclusion criteria will be excluded from this clinical study. In addition, any study subject who meets one or more of the following exclusion criteria will also be excluded from study enrollment:

Anesthesia Safety Products - Confidential Information

This document and the subject matter contained herein is the property of Anesthesia Safety Products and may not be copied, reproduced, or disclosed to others without the expressed written permission of a duly authorized agent of the company.

- 1.0 Study Subject's scheduled procedure involves the use of an infusion pump on the I.V. line that AirPurge will be attached to
- 2.0 Study Subject plans to participate or has participated in any other clinical trial within the 30 days prior to the start of the study.
- 3.0 Study Subject cannot be a homeless person, have an active drug/alcohol dependence or abuse history.

4.3 STUDY SUBJECT RECRUITMENT AND SCREENING

Study Subjects will be drawn from Clinical Sites' pediatric and adult patient populations who are scheduled to undergo one of the study procedures. Any study-specific recruitment materials will be reviewed by overseeing IRBs, if applicable. The *commercially available* FDA approved labeling materials may be utilized to explain the AirPurge device, based on Investigator preference.

4.4 EARLY WITHDRAWAL OF STUDY SUBJECTS

4.4.1 WHEN AND HOW TO WITHDRAW SUBJECTS

An Investigator may choose to discontinue a study subject from the study during the course of the procedure if in the opinion of the Investigator this action is in the best welfare of the study subject. If a study subject is withdrawn from the clinical study, this information will be recorded on the Operative Report including the reason for withdrawal. Subjects may also be withdrawn after the Eligibility Checklist / Demographics case report form has been completed based on Investigator judgment.

4.4.2 DATA COLLECTION FOR WITHDRAWN SUBJECTS

The Study Sponsor should be notified of any withdrawn study subjects and any completed CRFs submitted to the Study Sponsor with the reason for withdrawal.

4.4.3 STUDY SUBJECT DISCONTINUATION

Study subjects will be clearly informed during the Informed Consent process (*if applicable*) that they are free to withdraw from this post-approval study *after* they sign the Informed Consent Document and *before* their procedure. If this should occur, the Clinical Site should document the Study Subject's wish to discontinue their study participation by recording the date and reason for discontinuation (*if available*) on the study subject's Eligibility Checklist / Demographics form.

5.0 STUDY DEVICE

5.1 DESCRIPTION

The *commercially available* Class II AirPurge Air Detection and Removal System is comprised of the AirPurge Device (control unit) and disposable Cartridge. In this protocol they are referred to as the AirPurge System, the Device or the Cartridge.

The Study Sponsor will provide training on the recommended operation of the AirPurge System per ASP user training procedure; SOP-007, *prior to* the first study surgical procedure at each Clinical Site. Clinical Site personnel should read the "AirPurge™ System Quick Operating Instructions" and

Anesthesia Safety Products - Confidential Information

This document and the subject matter contained herein is the property of Anesthesia Safety Products and may not be copied, reproduced, or disclosed to others without the expressed written permission of a duly authorized agent of the company.

“AirPurge™ System – Air Detection and Removal System with Intravenous (I.V.) lines Operator’s Manual” thoroughly before use and have both readily available during device operation.

5.2 STANDARDIZED STUDY I.V. PARAMETERS / SET-UPS

The AirPurge System will be mounted to the “Active” I.V. line being used for maintenance and fluid replacement. The Intravenous Fluid and Flow Rate parameters will be standardized as follows for all study subjects:

I.V. Line: The AirPurge will be mounted to the free-flow, maintenance line
I.V. Fluid: Lactated Ringer’s or Blood

Fluid warmers may or may not be used based on each Clinical Site’s standard of care practices. The usage of a warmer and type of warmer will be recorded on the Operative Report.

Air filters may be used *below* the AirPurge based on each Clinical Site’s standard of care practices. Clinical Sites should follow their routine procedures for air bubble detection and elimination *below* the AirPurge.

During this post-approval study, the following Equipment Set-Ups should **not** be used with the intravenous line connected to the AirPurge System: infusion pumps, inflatable pressure cuffs, pressurized infusers, rapid infusion systems or catheters. Any boluses or syringe injections should be delivered **below** the AirPurge.

If at any point during the procedure, it is in the best interest of the patient’s welfare to modify this standard free-flow rate, the Investigator should proceed and record on the Operative Report, documenting the reason for modification. Deviation from the standardized flow will be categorized as a protocol deviation for analysis purposes.

5.3 PACKAGING

The reusable AirPurge Device(s) will be provided to each Clinical Site *prior to* the Site Initiation Visit and Clinical Site personnel training. An inventory of *single-use only* AirPurge Cartridges will be shipped *sterile* to Clinical Sites by Study Sponsor. Since the AirPurge is *not* investigational, *no* investigational device accountability process will be required. If any devices are damaged during shipment the Clinical Site will be instructed to notify the Study Sponsor.

5.4 CONTRAINDICATIONS

Do *not* use with fluids that are incompatible with standard I.V. lines.

5.5 WARNINGS

For a comprehensive description of *all* AirPurge System Warnings and Cautions refer to the “AirPurge™ System – Air Detection and Removal System with Intravenous (I.V.) lines Operator’s Manual”. Key study relevant Warnings are provided below:

a. The AirPurge System *cannot* purge air from I.V. extension line between AirPurge System and patient. The I.V. extension line must be cleared of air before connected to patient. Failure to clear

Anesthesia Safety Products - Confidential Information

This document and the subject matter contained hereon is the property of Anesthesia Safety Products and may not be copied, reproduced, or disclosed to others without the expressed written permission of a duly authorized agent of the company.

extension line could result in introduction of air to patient that could result in death or serious injury.

- b. Fluid warmers, if used, must be installed above the AirPurge.
- c. Mount the AirPurge lower than the infusion source, not higher than 4 feet (125 cm) and at or slightly below patient level. The I.V. pole should be vertical at all times
- d. The AirPurge will *not* reliably purge air at flow rates greater than 400 ml/minute
- e. Flow is diverted into the Collection Bag during air purging. Critical medication and contrast media should be injected *below* the AirPurge.

5.6 POWER

After plugging the AirPurge System into AC source, confirm all 3 battery lights are illuminated. Note: AC power (and *not* battery power) will be used for all study procedures.

5.7 MOUNTING THE DEVICE

Mount the AirPurge Device on the I.V. pole in a vertical position. Plug into AC outlet.

WARNING: The IV Pole must be kept vertical at all times. If the IV pole becomes non-vertical while the AirPurge System is in use, then:

-Check for air in the line connected directly to the study subject and take immediate and appropriate actions consistent with basic/standard I.V. practices.

-Check to see if any of the I.V. setup, tubing, equipment, has been damaged or disconnected; if yes, discontinue and restart the I.V. therapy set-up, as appropriate and consistent with basic/standard I.V. practices.

If the IV setup, tubing, and equipment, has not been damaged or disconnected, return the IV pole to a vertical position and check the functioning of the AirPurge System. If it is ON and not alarming then AirPurge System is removing all the air flowing into the AirPurge System.

5.8 INSTALLING THE CARTRIDGE

NOTE: Have "AirPurge™ System Quick Operating Instructions" available for a quick reference in the O.R. Handle according to your institution's procedures for sterile devices.

- a. Remove single-use Cartridge from sterile pouch. Collection Bag connector must be tight; **Blue** and **Green** caps mounted in place.
- b. Remove **Red** retaining clip; and discard. Open the Device Door. With **FRONT** of Cartridge facing you, push Cartridge onto pegs in the device. Close and latch the door.

5.9 SYSTEM START-UP / CLEARING THE LINES

CAUTION: Only use I.V. lines with Luer Lock connectors. When connecting the I.V. line to the top and bottom of Cartridge, do **not** over tighten Luer connections. Tighten connections **only** until slight resistance is felt.

- a. Remove **Green** inlet cap on top of Cartridge and connect primary I.V. to connector of Cartridge marked **IN**. Remove **Blue** outlet cap on bottom of Cartridge and connect the extension set to the connector at bottom of the Cartridge marked **OUT**. Ensure there are **no** kinks in any tubing.

Anesthesia Safety Products - Confidential Information

This document and the subject matter contained hereon is the property of Anesthesia Safety Products and may not be copied, reproduced, or disclosed to others without the expressed written permission of a duly authorized agent of the company.

- b. Turn the Device on. All front panel indicators (9) will illuminate for 3 seconds, then only the **ON** button and 3 battery lights (indicating AC power is present) will remain lit. If any other Indicator lights stay on or if there is an audible alarm, refer to Operator’s Manual and follow instructions. Record information regarding all indicators / alarms on the Operative Report.
- c. Start fluid flow for the primary I.V. lines. The Cartridge will fill with fluid; any air in line will be detected and diverted into the Collection Bag. When free of air, flow will then be diverted back to extension line. Once air free I.V. fluid clears the extension line, connect to the patient.

WARNING: The AirPurge System *cannot* purge air from I.V. extension line between AirPurge System and patient. The I.V. extension line must be cleared of air before connected to patient. Failure to clear extension line could result in introduction of air to patient that could result in death or serious injury.

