2.0 STUDY OBJECTIVES

2.1 PRIMARY STUDY OBJECTIVES

The primary objectives of this post-approval clinical study are:

- 1) to measure the *amount of air removed from the intravenous (I.V.) line by the AirPurge System* in a clinical setting with standardization of the surgical procedure, I.V. fluid and flow rate
- 2) to measure the *frequency and duration of the AirPurge purging mechanism activity* in a clinical setting with standardization of the procedure, I.V. fluid and I.V. line.

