3.0 STUDY DESIGN

3.1 GENERAL DESIGN

The AirPurge Air Detection and Removal System Post-Approval Multi-Center Clinical Study is a prospective, observational, single arm / non-randomized post-approval study design. This multi-center post-approval clinical study is *not* a comparative study design *nor* is the clinical design intended to support the functional safety and efficacy of the *commercially available* AirPurge System for the purposes of obtaining FDA approval. Therefore, there is *no* investigational device and *no* prospective safety / efficacy success criteria or endpoints. The AirPurge System will be utilized for the current FDA approved intended use / indications for use. The overall goal of this post-approval study is information gathering in regards to the clinical value of the AirPurge System within the operating room setting utilizing a set of controlled I.V. set-up parameters including I.V. fluid, I.V. line including the usage of key I.V. pole accessory equipment and a standardized group of procedures.

The study endpoint is the discontinuation of AirPurge System usage during the procedure and therefore there are *no* post-procedure follow-up requirements minimizing the risk of lost-to follow-up study subjects. Study subjects will be recruited from the Clinical Sites' current patient population scheduled to undergo one of the inclusion criteria procedures. Subjects will be enrolled into the study in a sequential manner.

Data collection is limited to two time points:

The hard copy CS001-12LL Eligibility Checklist / Demographics case report form (CRF) will be completed *prior to* surgery. Operative Day data will be collected utilizing two data collection methodologies as follows:

- 1) CS001-13LL Operative Report: This hard copy case report form (CRF) will be completed by Clinical Site personnel and collect information on device performance from the clinician's perspective, intravenous line fluid delivery specifics, and relevant background concerning the procedure.

Anesthesia Safety Products - Confidential Information

This document and the subject matter contained herein is the property of Anesthesia Safety Products and may not be copied, reproduced, or disclosed to others without the expressed written permission of a duly authorized agent of the company.

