5.14 INDICATORS AND ALARMS

Refer to page 13 of the AirPurge Operator’s Manual for further information on Indicators and Alarms. The incidence and timing of any Indicator Light or Alarm will be documented on the Operative Report.

Indicator	Alarm	Solution
TEMP	Yes	Discontinue Use. Turn Device Off and Open Door. Monitor Air Bubbles Manually & Contact ASP for Service.

Anesthesia Safety Products - Confidential Information

This document and the subject matter contained herein is the property of Anesthesia Safety Products and may not be copied, reproduced, or disclosed to others without the expressed written permission of a duly authorized agent of the company.

TURN OFF- OPEN DOOR	Yes	Discontinue Use. Turn Device Off and Open Door. Monitor Air Bubbles Manually & Contact ASP for Service.
DOOR	Yes	Ensure Cartridge is Inserted Correctly, Red Retaining Clip Removed & Door Securely Latched. If Alarm Persists Discontinue Use and Contact ASP for Service.
↑↑VERT	Yes	Reposition Device on I.V. Pole using Clamp. When Positioned Correctly Device Resets Itself.
PURGING	PURGING Indicator Lights when device Purging. After 1 minute (Indicator begins Blinking + Alarm)	DO NOT TURN OFF Device. Check I.V. Line for Obstructions or I.V. bag Empty* Very Low Flow Rates can Cause Purge Times > 1 Minute; Wait for Alarm to Silence.

*If Alarm persists discontinue use. Turn device off and open door. Monitor air bubbles manually and contact ASP for service.

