6.3 OPERATIVE REPORT

Visit 2 will involve Clinical Site personnel collection of the following data fields:

Subject ID #
Procedure Date
Procedure Start and End Time
AirPurge Start Time and End Time
Procedure (circle one): arterial septal defect closure, ballooning of coarctation, craniotomy, craniosynostosis, patent ductus arteriosus, (pda) closure, pulmonary artery stent deployment, pulmonary valve balloon dilatation, spinal fusion, scoliosis or cardiac surgery involving cardiopulmonary bypass
Procedure Complications
Use of Fluid Warmer
I.V. Fluid and Bag Volume
Additional I.V. Line Activity
Confirm AirPurge used on Free-flow maintenance line
AirPurge Waste Collection Bag
AirPurge Alarms
AirPurge Complaints

Anesthesia Safety Products - Confidential Information

This document and the subject matter contained herein is the property of Anesthesia Safety Products and may not be copied, reproduced, or disclosed to others without the expressed written permission of a duly authorized agent of the company.

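### Purges made while the line is being set up are not separated from later ones, so the purge-frequency summary can include activity from before the patient was connected

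*Combined protocol and SAP*

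**What the plan says.** - **Start-up (5.9).** The Device is turned on, then flow is started. The plan describes what follows: "The Cartridge will fill with fluid; any air in line will be detected and diverted into the Collection Bag". Connection comes last: "Once air free I.V. fluid clears the extension line, connect to the patient". The only recording instruction in this section is "Record information regarding all indicators / alarms on the Operative Report".
- **Restart (5.7).** If the pole tilts and the set-up is damaged or disconnected, staff are told to "discontinue and restart the I.V. therapy set-up, as appropriate and consistent with basic/standard I.V. practices". Set-up can therefore occur more than once in a case.
- **Objective 1 (2.1).** The quantity is the air "removed from the intravenous (I.V.) line by the AirPurge System" in a clinical setting. It is not limited to the time the patient is connected.
- **End of observation (3.1).** "The study endpoint is the discontinuation of AirPurge System usage during the procedure". No matching start is stated.
- **Times collected.** The Operative Report (6.3) lists "Procedure Start and End Time" and an AirPurge start and end time. The Data Monitor (6.4) records total powered-on time. Attachment 1 adds no connection time.
- **Indicators (5.14).** "The incidence and timing of any Indicator Light or Alarm will be documented on the Operative Report". PURGING is one of the tabulated indicators. Attachment 1 also places the timing of alarms and indicators among the Data Monitor data.
- **Analysis (7.0).** Air volume, purge duration and purge frequency are each summarised by mean, range and SD. Only the frequency item is tied to the question of how necessary purging is over a procedure. A time graph over the procedure and a correlation with clinical activity are also planned.

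**The concern.** A purge that clears a new line before connection tells the reader about priming. It does not show how often air arrives in a line already running into a patient. Section 7.0 wants the frequency summary to speak to the second question, but gives no rule that keeps the first kind of purge out. The study is descriptive, with no comparison and no success criteria, so these summaries are its results. A purge count whose starting point is unstated is hard to interpret, and most of all in subjects with few or no purges once connected. If one site takes AirPurge Start Time to be power-on and another takes it to be connection, and that field is used to cut the data, pooled counts will rest on different windows. A connection time not written down during the case cannot be reliably filled in later.

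**Working it through.** The plan gives no figure to reproduce, so the check is mainly one of text.

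**1. Are set-up purges expected?** Yes. In 5.9 power-on precedes flow, and flow with diversion of line air precedes connection. That the Data Monitor is already recording at that stage is an inference from its powered-on time and on/off counts in 6.4; the plan does not state it outright.

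**2. Do the listed times mark connection?** Three time spans can be formed:

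| Span | Source | Defined as the patient-connected period? |
|---|---|---|
| Procedure start to end | 6.3 | No |
| AirPurge start to end | 6.3 | No; neither end is defined in the list |
| Total time powered on | 6.4 | No |

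None of the three is so defined (0 of 3).

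**3. Does 7.0 select a window?** Not explicitly. The frequency item and the time graph both refer to the duration of the procedure, which points towards the first span. No cut-off is named, and nothing equates procedure start with connection.

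**4. Which summaries are affected?**
- Purge frequency: directly, because its stated purpose concerns need during the procedure.
- Interval between purges: possibly. The gap from the last set-up purge to the first connected purge would enter it.
- Time graph: possibly, depending on where its axis starts.
- Purge duration and air volume: they mix set-up and later activity, but 7.0 does not attach the necessity question to either.

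**5. Could the split be made afterwards?** In part. Timed indicators (Attachment 1), between-purge intervals and a time graph (7.0) all imply timed purges. Clock time is not stated outright. Nor is a subject identifier listed among the Data Monitor fields in 6.4, although 10.5 puts the subject ID on both paper forms. Section 6.1 has the Data Monitor collected when a site finishes, with optional periodic checks, and 3.3 allows up to 50 subjects per site. Matching records to subjects may therefore depend on the handwritten times.

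**6. Size.** The documents give no line or Cartridge volume, no set-up flow rate and no number of set-up purges, so no total effect on count, duration or volume can be computed. As an illustration only, let n be the purges while connected (assumed range 0 to 20) and suppose one set-up purge is counted. The reported count is n + 1 and the relative increase is 1/n:

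| n | Reported | Increase |
|---|---|---|
| 0 | 1 | not defined |
| 1 | 2 | 1/1 = 100% |
| 5 | 6 | 1/5 = 20% |
| 10 | 11 | 1/10 = 10% |
| 20 | 21 | 1/20 = 5% |

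This shows the effect of one purge. It does not estimate how many occur.

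**The case against.** The best defence is that the plan already holds most of what is needed. Attachment 1 puts indicator timing in the Data Monitor data, and PURGING is an indicator. The intervals and the graph need timed purges. With the recorded procedure start, any purge before that time could be set aside without a new field. The Operative Report also records purging activity and additional line activity, and 7.0 plans to relate purging to clinical events. The restart in 5.7 is a contingency. The form, the Operator's Manual and the training procedure may define the times more closely. Preferring the connected period to the procedure is also a choice of target, since no objective mentions connection.

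Much of this stands, and it lowers the weight of the point. Two things remain. Procedure start is only an approximate cut-off, because it need not coincide with connection and 7.0 does not adopt it. And a definition on the form would still leave 7.0 without a rule for set-up purges.

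A reader might go further and infer that all three summaries overstate the need for purging, or that the result for objective 1 is wrong. The documents do not support either. The necessity question is attached to frequency alone, and objective 1 concerns air removed from the line, which properly includes air cleared at set-up.

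**Conclusion.** The point holds and is minor. As written, the frequency summary meant to show the need for purging during a procedure can count purges made before the patient was connected, and the interval and time-graph results may be affected in the same way. Total air under objective 1 is valid as measured but combines two different sources. A reader might also infer that set-up activity can never be separated; that is too strong, because timed records and procedure start probably allow an approximate split.

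The size is unknown. The counts shown for one set-up purge rest on an assumed range of connected purges. The conclusion assumes that the Data Monitor records from power-on, and it rests on the field lists, because the case report form, Operator's Manual and training procedure were not available.

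**What to change.** Before enrolment:

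1. Define AirPurge Start Time as Device power-on and AirPurge End Time as discontinuation of AirPurge use, matching 3.1.
2. Add one field to the Operative Report and Attachment 1: the clock time at which the line is connected to the patient, repeated if the set-up is restarted.
3. Confirm that Data Monitor purges carry clock times that can be matched to the subject.
4. In 7.0, report purge count, purge duration and air volume separately before and after connection. Use the post-connection period for the necessity question and the time graph, and keep set-up air as its own result under objective 1.

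The cost is two definitions, one extra handwritten time per case (more if the set-up is restarted) and a split of the Data Monitor record in the analysis. Alignment will be only as accurate as the handwritten times, and the headline purge count will be smaller if set-up purges occur. Clinical management is unchanged.
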